5.6.6 Columbia-Suicide Severity Rating Scale

C-SSRS evaluations are tabulated as described in the CTP Section 14.3.9.5. To clarify, occurrences of the composite event ‘Any suicidal ideation or behaviour during the trial’ will be derived from categories 1 to 9, and occurrences of the composite event ‘Suicidal behaviour’ will be derived from categories 6 to 9, in accordance with CTP Section 11.5.2.

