5.4 Ethical considerations

This trial will be conducted in accordance with the ethical principles that have their origins in International Council for Harmonisation Good Clinical Practice (ICH GCP) guidelines in compliance with the approved protocol and applicable regulatory requirements.

In accordance with the current version of ICH GCP guidelines, qualified medical personnel employed by LEO Pharma will be readily available to advise on trial-related medical questions. Medical monitoring will be performed throughout the trial.

In this trial, all subjects will be treated with biologic medications approved in EU for the treatment of moderate-to-severe plaque psoriasis. Since the trial has no placebo arm, any ethical considerations regarding withholdment of treatment do not apply.

No children or other vulnerable subjects incapable of giving informed consent will be included in this clinical trial. Pregnant or breastfeeding women and women trying to conceive will not be included in the trial. Women of childbearing potential must agree to use a highly effective method of contraception to prevent pregnancy during the clinical trial and until 12 weeks after discontinuation of treatment with investigational medicinal product (IMP). In addition, all women of childbearing potential will have a pregnancy test performed before, during, and after trial procedures to minimise the risk of foetuses being exposed to the IMPs.

Suicidal ideation and behaviour (SIB), including completed suicide, have been reported in patients treated with brodalumab. The majority of patients with suicidal behaviour had a history of depression and/or suicidal ideation or behaviour. A causal association between treatment with brodalumab and increased risk of SIB has not been established (14).

Since a history of prior depression and/or SIB are known risk factors for new SIB events (15), subjects with a recent history of depression (within 2 years), Patient Health Questionnaire-8

THIS DOCUMENT CONTAINS CONFIDENTIAL INFORMATION AND MUST NOT BE COPIED OR MADE AVAILABLE TO ANY THIRD PARTY WITHOUT THE PRIOR WRITTEN CONSENT OF THE LEO PHARMA GROUP

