11.5.2 Columbia-Suicide Severity Rating Scale

The C-SSRS is a rater-administered, standardised, and validated instrument developed for the assessment of the severity and frequency of SIB (26, 27).

The C-SSRS is divided into suicidal ideation (category 1 to 5), suicidal behaviour (category 6 to 9), completed suicide (category 10), and non-suicidal self-injurious behaviour:

Suicidal ideation

- Category 1: Wish to be dead.
- Category 2: Non-specific active suicidal thoughts.
- Category 3: Active suicidal ideation with any methods (not plan) without intent to act.
- Category 4: Active suicidal ideation with some intent to act, without specific plan.

THIS DOCUMENT CONTAINS CONFIDENTIAL INFORMATION AND MUST NOT BE COPIED OR MADE AVAILABLE TO ANY THIRD PARTY WITHOUT THE PRIOR WRITTEN CONSENT OF THE LEO PHARMA GROUP

- Category 5: Active suicidal ideation with specific plan and intent.

Suicidal behaviour

- Category 6: Preparatory acts or behaviour.
- Category 7: Aborted attempts.
- Category 8: Interrupted attempts.
- Category 9: Actual attempts (non-fatal).

Completed suicide

- Category 10: Completed suicide.

Non-suicidal self-injurious behaviour

- Non-suicidal self-injurious behaviours.

At all visits where the C-SSRS interview must be performed (see Section 4), it must be done after all other visit activities have been completed. However, the C-SSRS interview must be performed and the answers reviewed before the IMP administration. The C-SSRS takes approximately 3 to 10 minutes to complete.

The investigator must evaluate the subject's eligibility in relation to exclusion criteria no. 11 and 12 for the C-SSRS components 'history of suicidal behaviour' and 'suicidal ideation' at screening (Visit 1) and baseline (Visit 2; Week 0).

The 'baseline' paper version of the C-SRSS will be used at screening and the 'since last visit' paper version will be used at all subsequent visits. The C-SSRS assessments will be transcribed into the eCRF.

Subjects with suicidal ideation of category 4 or 5 or any suicidal behaviour must be referred to a mental health professional and be discontinued from IMP. In addition, the event must be reported as an AE.

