14.3.9.5 Columbia-Suicide Severity Rating Scale

The most severe C-SSRS response observed for each subject over the relevant time periods will be summarised by the number and percentage of subjects, as well as by treatment arm based on the safety analysis set. This includes the time periods ‘while exposed to IMP’, ‘while in trial’, ‘while exposed to IMP and blinded’, and ‘while in trial and blinded’. The severity of the response will be ranked in the following order, from least to most severe:

1. Wish to be dead.
2. Non-specific active suicidal thoughts.
3. Active suicidal ideation with any methods (not plan) without intent to act.
4. Active suicidal ideation with some intent to act, without specific plan.
5. Active suicidal ideation with specific plan and intent.
6. Preparatory acts or behaviour.
7. Aborted attempt.
8. Interrupted attempt.

THIS DOCUMENT CONTAINS CONFIDENTIAL INFORMATION AND MUST NOT BE COPIED OR MADE AVAILABLE TO ANY THIRD PARTY WITHOUT THE PRIOR WRITTEN CONSENT OF THE LEO PHARMA GROUP

9. Actual attempt (non-fatal).

10. Completed suicide.

Additionally, the number and percentage of subjects reporting the following composite events will be presented by treatment arm:

- Any suicidal ideation or behaviour during the trial.
- Suicidal ideation with intent to act (4-5).
- Suicidal behaviour.
- Suicidal ideation (4-5) and suicidal behaviour.
- Suicidal ideation (4-5) or suicidal behaviour.
- Self-injurious behaviour without suicidal intent.

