14.3.6.2 Estimand strategy for binary endpoints	When imputing missing IGA values, full-data imputation will be used as opposed to producing monotone missingness as an intermediate step	To simplify, since full-data imputation based on fully conditional specification methods is readily available in PROC MI.
14.3.6.2 Estimand strategy for binary endpoints	The CTP specifies a supplementary analysis of the primary estimand for binary endpoints, which only uses assessments performed at on-site visits. This supplementary analysis will not be done.	Based on a blind review of data, there have only been very few remote assessments during the trial and, none of the endpoints that are specified to undergo the supplementary analysis have been remotely assessed.

THIS DOCUMENT CONTAINS CONFIDENTIAL INFORMATION AND MUST NOT BE COPIED OR MADE AVAILABLE TO ANY THIRD PARTY WITHOUT THE PRIOR WRITTEN CONSENT OF THE LEO PHARMA GROUP

14.3.6.2 Estimand strategy for binary endpoints and 14.3.6.4 Estimand strategy for continuous endpoints	As part of a sensitivity analysis, the CTP specifies imputation of missing data based on a 'retrieved-data' pattern-mixture model if sufficient data exist. This part of the sensitivity analysis will not be performed.	Sufficient data for fitting the 'retrieved-data' pattern-mixture model cannot be expected due to the decision of ending the trial ahead of schedule.
14.3.6.3 Estimand strategy for time-to-event endpoints	The sensitivity analysis with respect to the assumption of non-informative censoring will not be performed	A blind review of data has shown that no event time has been censored for another cause than administrative censoring.

Abbreviations: CTP = clinical trial protocol; IGA = Investigator's Global Assessment; IMP = investigational medicinal product; PASI = Psoriasis Area and Severity Index; PASI 100 = 100% improvement from baseline in PASI score; TNF- α = tumour necrosis factor- α .

7 Supporting documentation

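### SAP 5.6.6 derives the C-SSRS composites from categories 1–9 and 6–9, so a subject whose only recorded category is completed suicide (10) falls in none of the six (minor, latent)

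*SAP*

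**What the plan says.** Protocol 11.5.2 divides the C-SSRS into ideation (categories 1–5), "suicidal behaviour (category 6 to 9), completed suicide (category 10") and non-suicidal self-injury. Category 9, actual attempt, is restricted to non-fatal attempts.

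Protocol 14.3.9.5 plans two displays by arm. The first is the most severe response per subject, ranked from "1. Wish to be dead" up to "10. Completed suicide". The second is a set of six composite rows. One of these, "Suicidal ideation (4-5) or suicidal behaviour", combines two of the others. The protocol gives category numbers only for ideation (4–5); it gives none for the 'any' row or for suicidal behaviour.

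SAP 5.6.6 supplies the two missing ranges. The composite for any ideation or behaviour "will be derived from categories 1 to 9, and occurrences of the composite event" for suicidal behaviour "will be derived from categories 6 to 9, in accordance with CTP Section 11.5.2". It says nothing further about the two rows that combine ideation 4–5 with behaviour.

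Protocol 5.4 uses the umbrella term more widely: "Suicidal ideation and behaviour (SIB), including completed suicide, have been reported in patients treated with brodalumab".

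**The concern.** Both SAP ranges stop at 9. Category 9 excludes fatal attempts by definition, so a completed suicide cannot enter a composite through that category, and no composite names category 10. The row a reader is most likely to take as the suicidality total, the one labelled as any ideation or behaviour, would count a passive wish to be dead and leave out a suicide.

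Suicidality is a named safety topic in this protocol. It drives exclusion criteria 11–14, C-SSRS and PHQ-8 monitoring throughout treatment, and mandatory stopping of IMP. A summary row on that topic should not be able to omit the gravest event its label covers. At stake is the correctness of descriptive safety counts. No hypothesis test or estimand uses these rows.

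**Working it through.** The plan states no figure to reproduce, so the check is an enumeration of row membership.

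**Inputs.** The six composites are those of protocol 14.3.9.5:

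1. any ideation or behaviour: categories 1–9 (SAP 5.6.6)
2. ideation with intent: categories 4–5 (the row's own label)
3. suicidal behaviour: categories 6–9 (SAP 5.6.6)
4. ideation 4–5 **and** behaviour: row 2 and row 3
5. ideation 4–5 **or** behaviour: row 2 or row 3
6. self-injury without suicidal intent: outside categories 1–10

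Rows 4 and 5 are taken to use the same 6–9 set as row 3 because they use the same term. This is an inference, since the SAP gives ranges for rows 1 and 3 only.

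**Rule.** A subject counts in a row if any recorded category lies in that row's set.

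| Recorded categories | Rows under SAP ranges | Rows with 1–10 and 6–10 | Rows gained |
|---|---|---|---|
| one of 1–3 only | 1 | 1 | 0 |
| 4 or 5 only | 1, 2, 5 | 1, 2, 5 | 0 |
| one of 6–9 only | 1, 3, 5 | 1, 3, 5 | 0 |
| 10 only | none | 1, 3, 5 | 3 |
| one of 1–3, and 10 | 1 | 1, 3, 5 | 2 |
| 4 or 5, and 10 | 1, 2, 5 | 1, 2, 3, 4, 5 | 2 |
| one of 6–9, and 10 | 1, 3, 5 | 1, 3, 5 | 0 |

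Category 10 is the only one of the ten that, recorded alone, falls in no composite. Extending the ranges leaves every subject without category 10 unchanged. Row 4 (the 'and' row) changes only when ideation 4–5 was recorded as well and no category 6–9 was.

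**Size of one event.** 1 divided by the number of subjects in the arm. At the planned 120 per arm, 1/120 = 0.0083, or 0.8%. SAP Section 6 (Panel 22) says the trial was ended ahead of schedule and no achieved arm size is given, so the percentage would be larger if the arm is smaller.

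**Could such an event have occurred?** Panel 22 reports: "A blind review of data has shown that no event time has been censored for another cause than administrative censoring". SAP 5.3 handles a death by the strategy used for discontinuation due to pandemic restrictions, and SAP 5.4.2 turns that into right censoring. A death in a subject still at risk in the time-to-event analysis would therefore be non-administrative censoring, and none was found. But that analysis uses the FAS, which requires a post-baseline PASI assessment, while the C-SSRS tables use the safety set of all dosed subjects. The statement therefore leaves open a death after response, a death after discontinuation of IMP, and a death in a dosed subject outside the FAS.

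**The case against.** The strongest reply is that the SAP applies the protocol's own definition. Protocol 11.5.2 sets behaviour at 6–9 and makes completed suicide its own class. Exclusion criterion 11 lists the same four acts as suicidal behaviour, and the ranking in 14.3.9.5 also keeps category 10 separate. The sentence in 5.4 is background, not an analysis definition. This stands for the 6–9 range. A reader might infer that the SAP contradicts the protocol there, and it does not. It does not settle the 'any' row: 11.5.2 defines no such composite, 14.3.9.5 gives it no range, and the only protocol text on whether the umbrella term covers completed suicide says that it does. Criterion 11 concerns living candidates and does not bear on how a fatal outcome is tabulated.

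Second, the event is reported elsewhere: as rank 10 in the most-severe-response table over four time periods, in the death and SAE summaries with a narrative, and among the AESIs. This also stands. A reader might infer that a suicide would disappear from the report, and the documents do not support that. Reporting it elsewhere limits the consequence but does not correct a row whose label covers more than its derivation counts. Nor does any fixed disagreement with the AESI table follow: AESIs come from an eCRF flag (SAP 5.6.2) and the composites from C-SSRS categories.

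Third, the C-SSRS is a rater-administered interview, and the documents do not say how category 10 is entered for a subject who has died. This is a fair limit on how likely the category-10-only record is. Protocol 14.3.9.5 nevertheless plans for category 10 as a recordable response.

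**Conclusion.** The point holds as a minor, latent defect. Under the SAP ranges a subject with category 10 alone is counted in 0 of 6 composites, against 1 for category 1 alone and 3 for any single category from 4 to 9. The result for rows 1 and 3 follows directly from SAP 5.6.6; for rows 4 and 5 it rests on their sharing the same meaning of suicidal behaviour.

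The effect is confined to descriptive rows and is zero if no completed suicide occurred. The documents do not say whether one did. A reader might take the blind-review statement in Panel 22 as proof that none occurred. It makes a death less likely but does not exclude one, because it covers only event times in the FAS.

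**What to change.** In SAP 5.6.6:

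- Derive the composite for any ideation or behaviour from categories 1–10, and suicidal behaviour from 6–10.
- State that the two composites combining ideation 4–5 with behaviour use the same 6–10 set.
- Replace the bare reference to protocol 11.5.2 with a note that completed suicide, a separate class there, is deliberately included. Add an entry to Panel 22 if this is judged a change from the protocol.
- Keep the separate category 10 row in the most-severe-response table.

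If the sponsor prefers to keep 6–9 for suicidal behaviour, the minimum is to extend the 'any' row to 1–10 and add a composite row for completed suicide. A category-10-only subject would then be counted in those two rows.

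The cost is a few lines of SAP text and a small change to the derivation. Counts for subjects without category 10 stay as they are.

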5.6.7 Patient Health Questionnaire-8

PHQ-8 evaluations are tabulated as described in the CTP Section 14.3.9.6.

5.7 Interim analysis

No interim analysis is planned.

THIS DOCUMENT CONTAINS CONFIDENTIAL INFORMATION AND MUST NOT BE COPIED OR MADE AVAILABLE TO ANY THIRD PARTY WITHOUT THE PRIOR WRITTEN CONSENT OF THE LEO PHARMA GROUP

6 Changes to analyses described in the protocol

[Panel 22](#) summarises the changes to the analyses planned in the protocol.

Panel 22. Changes to analyses planned in the protocol

Section in CTP	Description of change	Brief rational
6 Trial objectives, endpoints, and estimands	
Panel 1 lists the additional exploratory endpoints,
 
 Having PASI 100 response, assessed separately at Weeks 1, 2, 6, 10, 12, and 14, Having IGA of 0, assessed separately at Weeks 4, and 8, Having IGA of 0 or 1, assessed separately at Weeks 4, and 8, Having IGA of 0 or 1 and at least a 2-grade improvement from baseline, assessed separately at Weeks 4, and 8, 
which are not described in the CTP.
 
Analyses of the above mentioned endpoints have been specified to be carried out in Panel 10.
	The additional exploratory endpoints, and the analyses of them, have been specified to obtain additional insights from the collected data on the onset of action for the IMPs.
14.3.7 Analysis of efficacy endpoints		
6 Trial objectives, endpoints, and estimands	
The explorative endpoints described in the CTP,
 
 Having absolute PASI ≥ 3, assessed separately at Weeks 4, 8, 16, and 28 Having absolute PASI ≥ 5, assessed separately at Weeks 4, 8, 16, and 28, 
have been replaced by the respective exploratory endpoints
 
 Having absolute PASI ≤ 3, assessed separately at Weeks 4, 8, 16, and 28 Having absolute PASI ≤ 5, assessed separately at Weeks 4, 8, 16, and 28. 	To align with all other endpoints, where response to the endpoint indicates treatment success.
14.3.7 Analysis of efficacy endpoints	The above-described replacements have also been implemented in Panel 10 .	

THIS DOCUMENT CONTAINS CONFIDENTIAL INFORMATION AND MUST NOT BE COPIED OR MADE AVAILABLE TO ANY THIRD PARTY WITHOUT THE PRIOR WRITTEN CONSENT OF THE LEO PHARMA GROUP

6 Trial objectives, endpoints, and estimands	Note 4) to Panel 2 clarifies that the population components of estimands based on PP-PASI or PP-IGA only include subjects with palmoplantar psoriasis. Likewise, the population components of estimands based on sPGA-G only include subjects with genital psoriasis.	PP-PASI is used to quantify the area and severity of palmoplantar psoriasis, so treatment effects based on this tool are not of interest for subjects without palmoplantar psoriasis. This is also aligned with the protocol-specified procedure that only subjects with palmoplantar psoriasis at baseline will be followed post randomisation. Likewise for PP-IGA and sPGA-G.
14.2 Trial analysis sets	It has been clarified that analyses of endpoints based on PP-PASI or PP-IGA will be based on the FAS restricted to those subjects who have a positive PP-PASI score at baseline. Likewise for analyses of endpoints based on sPGA-G.	
14.3.6 Estimand strategy	
Prior TNF-α inhibitor use at baseline ($\leq 1, > 1$) will not be included as a factor in any analysis model. This also means that interactions with prior TNF-α inhibitor use at baseline ($\leq 1, > 1$) will not be included in the sensitivity analysis model described in Section 5.4.1.2.2.
	
Amendment 3 of the CTP introduced changes to the eligibility criteria and handled these changes in the analysis by including prior TNF-α inhibitor use at baseline ($\leq 1, > 1$) as a factor in all analysis models.
 
However, the decision to end the trial ahead of schedule was made shortly after implementing Amendment 3 of the CTP, and very few subjects can be expected to have been randomised under the amended eligibility criteria. In particular, very few randomised subjects can be expected to have used more than one TNF-α inhibitor at baseline, so we do not consider the adjustment for prior TNF-α inhibitor use at baseline ($\leq 1, > 1$) feasible.

THIS DOCUMENT CONTAINS CONFIDENTIAL INFORMATION AND MUST NOT BE COPIED OR MADE AVAILABLE TO ANY THIRD PARTY WITHOUT THE PRIOR WRITTEN CONSENT OF THE LEO PHARMA GROUP

14.3.6 Estimand strategy	In procedures for multiple imputation, the CTP specifies the number of imputations to be 1000. Instead, the number of imputations will be 250.	To align with the number of imputations specified for other brodalumab trials, LP0160-1329 and LP0160-1396. 250 imputations substantially exceed the default number of imputations NIMPUTE=25 for PROC MI, and will for sure exceed the percentages of cases with missing values (described as a rule of thumb for the number of imputations in the SAS/STAT 15.2® User's Guide for PROC MI).
14.3.6.2 Estimand strategy for binary endpoints	The procedures for multiple imputation of missing data have been slightly changed: In case of PASI 100 response at Week 16, the CTP describes part of the procedure as a stepwise imputation of underlying PASI scores, sequentially for Weeks 2, 4, 6, 8, 10, 12, 14, and 16. This stepwise process has been changed to also include imputation of underlying PASI scores for baseline and Week 1. A similar change has been made to the analogous stepwise procedure for imputing underlying IGA values.	To handle instances of missing baseline values, to accommodate the above-described addition of the explorative endpoint 'having PASI 100 response at Week 1' and to make use of the data collected at Week 1 in the imputation of missing data.
14.3.6.2 Estimand strategy for binary endpoints	When imputing missing IGA values, full-data imputation will be used as opposed to producing monotone missingness as an intermediate step	To simplify, since full-data imputation based on fully conditional specification methods is readily available in PROC MI.
14.3.6.2 Estimand strategy for binary endpoints	The CTP specifies a supplementary analysis of the primary estimand for binary endpoints, which only uses assessments performed at on-site visits. This supplementary analysis will not be done.	Based on a blind review of data, there have only been very few remote assessments during the trial and, none of the endpoints that are specified to undergo the supplementary analysis have been remotely assessed.

THIS DOCUMENT CONTAINS CONFIDENTIAL INFORMATION AND MUST NOT BE COPIED OR MADE AVAILABLE TO ANY THIRD PARTY WITHOUT THE PRIOR WRITTEN CONSENT OF THE LEO PHARMA GROUP

14.3.6.2 Estimand strategy for binary endpoints and 14.3.6.4 Estimand strategy for continuous endpoints	As part of a sensitivity analysis, the CTP specifies imputation of missing data based on a 'retrieved-data' pattern-mixture model if sufficient data exist. This part of the sensitivity analysis will not be performed.	Sufficient data for fitting the 'retrieved-data' pattern-mixture model cannot be expected due to the decision of ending the trial ahead of schedule.
14.3.6.3 Estimand strategy for time-to-event endpoints	The sensitivity analysis with respect to the assumption of non-informative censoring will not be performed	A blind review of data has shown that no event time has been censored for another cause than administrative censoring.

Abbreviations: CTP = clinical trial protocol; IGA = Investigator's Global Assessment; IMP = investigational medicinal product; PASI = Psoriasis Area and Severity Index; PASI 100 = 100% improvement from baseline in PASI score; TNF- α = tumour necrosis factor- α .

7 Supporting documentation

7.1 Appendix 1: Disposition of subjects

An overall summary of subject disposition will be presented. The disposition summary will include information on the number of subjects screened, randomised, exposed, included in the FAS, permanently discontinuing IMP, and withdrawing from the trial by treatment arm and overall.

Stacked cumulative incidence plots of the time to permanent discontinuation of IMP and withdrawal from trial will be presented separately for the ITT analysis set by treatment arm and reason. These analyses have been elaborated on below.

[figure not shown]
